9.7. Data sources

For this pilot study, the data in Table 9.3 from C4181001 and C4181005 will be pooled to create a single dataset. With respect to patients the component datasets will be mutually exclusive – that is, there are no patients common to both studies.

This retrospective cohort external control arm study will include achondroplasia patients from Study C4181005 and those from Study C4181001 who meet the inclusion and exclusion criteria of Study C4181005. Study C4181005 is a single-arm trial to evaluate the safety and tolerability of recifercept doses and dosing regimen, and efficacy to increase height growth in achondroplasia patients. Study C4181005 will include approximately 63 children with achondroplasia aged 3 months to 10 years (inclusive) with Tanner Stage 1, who are enrolled and randomized to receive one of three doses of recifercept (1mg/kg onceweekly, 2mg/kg twice-weekly, or 1.5mg/kg once-daily) subcutaneously for 12 months. Demographics, medical history, anthropometric measurements, and patient-reported outcomes in functional status and quality of life are collected approximately every 3 months. Study C4181001 is a prospective natural history study to collect the longitudinal anthropometric and disease-related complication data in children with achondroplais. It will

PFIZER CONFIDENTIAL

CT24-WI-GL02-RF02 3.0 Non-Interventional Study Protocol Template For Secondary Data Collection Study 23-May-2022 Page 23 of 26 Recifercept C4181010 NON-INTERVENTIONAL STUDY PROTOCOL V1.1, Nov 09, 2023 include approximately 300 achondroplasia patients aged 0-15 years with Tanner Stage I recruited from global sites. Patient data will be collected at baseline and at every 3-month interval visits, for a maximum of 5 years. Further details on data sources are presented in Table 2.

9.8. Quality control

Quality control procedures are described in the protocols of Study C4181001 and Study C4181005. No additional quality control will be performed in this study.

9.9. Limitations of the research methods

There are several limitations to this study. Externally controlled studies do not rely on randomization, resulting in inherent bias and a potential lack of comparability between treated and untreated groups (Tjiete & Brouder, 2010)(6). We will apply the same inclusion and exclusion criteria to select patients in the external control arm and use propensity score methodology to adjust for the differences between patients included in the Study C4181005 and patients as external controls. However, depending on the extent of data collection in Study C4181001 and Study C4181005, the propensity score modeling may not adjust for all potential confounders. Additionally, even though Study C4181001 is a multi-country study, patients included in Study C4181001 and Study C4181005 may not represent the entire achondroplasia patient population, and generalizability of study results may be limited.

9.10. Other aspects

Not applicable.

10. PROTECTION OF HUMAN SUBJECTS

10.1. Patient information

This study involves data that exist in anonymized structured format and contain no patient personal information.

10.2. Patient consent

As this study involves anonymized structured data, which according to applicable legal requirements do not contain data subject to privacy laws, obtaining informed consent from patients by Pfizer is not required.

10.3. Institutional review board (IRB)/Independent ethics committee (IEC)

Not applicable.

10.4. Ethical conduct of the study

The study will be conducted in accordance with legal and regulatory requirements, as well as with scientific purpose, value and rigor and follow generally accepted research practices

PFIZER CONFIDENTIAL CT24-WI-GL02-RF02 3.0 Non-Interventional Study Protocol Template For Secondary Data Collection Study 23-May-2022 Page 24 of 26 Recifercept C4181010 NON-INTERVENTIONAL STUDY PROTOCOL V1.1, Nov 09, 2023 described in Guidelines for Good Pharmacoepidemiology Practices (GPP), The ENCePP Code of Conduct for scientific independence and transparency in the conduct of pharmacoepidemiological and pharmacovigilance studies, FDA Guidance for Industry: Good Pharmacovigilance Practices and Pharmacoepidemiologic Assessment (7–9).

11. MANAGEMENT AND REPORTING OF ADVERSE EVENTS/ADVERSE REACTIONS

This study involves data that exist as structured data by the time of study start. In these data sources, individual patient data are not retrieved or validated, and it is not possible to link (i.e., identify a potential association between) a particular product and medical event for any individual. Thus, the minimum criteria for reporting an adverse event (AE) (i.e., identifiable patient, identifiable reporter, a suspect product, and event) cannot be met.

12. PLANS FOR DISSEMINATING AND COMMUNICATING STUDY RESULTS

In the event of any prohibition or restriction imposed (e.g., clinical hold) by an applicable competent authority in any area of the world, or if the investigator is aware of any new information which might influence the evaluation of the benefits and risks of a Pfizer product, Pfizer should be informed immediately.

14. LIST OF TABLES

Table 1. Sample size and power calculation

Table 2. Data sources

Table 3. Listing of all variables of importance

15. LIST OF FIGURES

Figure 1. Sample Size

16. ANNEX 1. LIST OF STAND ALONE DOCUMENTS

None.

17. ANNEX 2. ENCEPP CHECKLIST FOR STUDY PROTOCOLS

Not applicable.

18. ANNEX 3. ADDITIONAL INFORMATION

Not applicable.

1 AMENDMENTS FROM PREVIOUS VERSION(S)

This amendment to the version 1 for the SAP will take place after last subject, last visit. Changes to the SAP include:

- 1. Height Growth will be excluded as a study objective (Section 2.3): Height Growth was specified as the primary endpoint in concordance with the primary endpoints from C4181005; however the definition of height growth is inappropriate as an endpoint for this protocol. For C4181005, there are no placebo/comparator arms as part of that trial. In C4181010 there is an arm considered as placebo. Height growth is a ratio of observed versus expected change from baseline for anthropometric endpoints using historical controls. In this setting that would necessitate formulation of a Cauchy random variable.
- 2. Section 2.1 revised to reflect binary treatment group
- 3. Safety Endpoints are removed (Sections 5.2): All safety endpoints for this study can be reviewed by perusing the original CSRs for C4181005 (for treated patients) and C4181001 (for untreated patients).
- 4. Achondroplasia & PRO endpoints are removed (Section 5.3)
- 5. Statistical Hypothesis uses Height Z-score instead for Height Growth (Section 3.1)
- 6. Age and gender are removed as covariates (Section 5.4)
- 7. Height Z-Score replaces Height growth (section 7.2.2)
- 8. AGV is removed from Appendix
- 9. Height Z-Score replaces Height growth (section 7.2.4)
- 10. All Bayesian method exploration are removed (section 7.2.1)
- 11. Safety analyses removed (section 7.2.3)
- 12. "Proportion of patients reaching Height Growth Threshold ≥ 1.5 " analysis is removed (section 7.2.4)
- 13. SAS Code for Statistical Analysis added to section 10.3
- 14. Analyses of Achondroplasia-Related Complications and PRO endpoints for Objective 2 are removed.

2 INTRODUCTION

- Note: in this document, any text taken directly from the non-interventional (NI) study protocol is *italicised*.
- Achondroplasia is a heritable autosomal dominant disorder and is the most common form of skeletal dysplasia in humans, with a global birth prevalence of 1 in 25-30,000 or ~250,000 individuals worldwide (1–3). Achondroplasia is caused by a single-point gain-of-function mutation in the gene encoding the fibroblast growth factor receptor 3 (FGFR3) (2,4). FGFR is a key inhibitory regulator of endochondrial ossification and its over-activiation interferes with normal chondrocyte maturation and causes shorter long bones and changes in flat bones such as the occipital bone and vertebrae.

- Achondroplasia results in short stature and a range of severe complications due to abnormal ossification centers in the cranial base, facial bones, vertebrae, rib cage, and joints. Lordosis, kyphosis, small foramen magnum, and spinal stenosis are the most common achondroplasia-related orthopaedic complications. Other achondroplasia related complications include sleep-disordered breathing, otitis media, and hydrocephalus. Medical complications associated with achondroplasia greatly impact physical and psychosocial functioning, self-esteem, and patient quality of life (3,5).
- Currently, vosoritide is the only treatment approved by EMA (for achondroplasia patients aged 2 years and older with open growth plates) and FDA (for achondroplasia patients aged 5 years and older with open growth plates) to increase linear growth. It is an analog of C-type natriuretic peptide and works by binding to a receptor called natriuretic peptide receptor type B (NPR-B), which reduces the activity of FGFR3. Other available treatments are either aimed at limb lengthening with surgery or are interventions to treat the complications associated with achondroplasia. Recifercept is a modified soluble recombinant human FSFR3 under development for the treatment of achondroplasia. Recifercept is designed to be a decoy protein, competing for ligands of the FGFR3-G380R receptor responsible for achondroplasia and by forming inactive heterodimers with FGFR3 monomers. By binding free FGFR3-activating ligands and forming inactive dimers, recifercept reduces activation of the receptor, allowing chondrocyte proliferation and differentiation to proceed.
- A recifercept phase 2 clinical study (Study C4181005) is ongoing to investigate the safety, tolerability, pharmacokinetics (PK) and efficacy of recifercept in children aged 3 months to 10 years with achondroplasia. Fifty-four eligible participants aged 2-10 years and 9 patients aged 3 months to 2 years will be enrolled and randomized to receive one of three doses of recifercept subcutaneously (Img/kg once-weekly, 2mg/kg twice weekly, or 1.5mg/kg once-daily, n=21 per dose). Once participants complete the phase 2 trial, they will be offered enrollment into an open-label extension study at the dose previously received in the phase 2 trial or at the therapeutic dose once it is identified. A separate multi-country prospective observational natural history study (Study C4181001) is ongoing to examine the anthropometric characteristics, and achondroplasia. A total of 300 achondroplasia patients aged 0 and 15 years of age will be recruited and followed up for a duration of 5 years. All patients participating in Study C4181005 were or will be recruited from Study C4181001.

2.1 STUDY DESIGN

• This is a retrospective cohort study using existing data from two ongoing studies: C4181001 and C4181005. The study population will include two independent study

PFIZER CONFIDENTIAL

CT24-WI-GL03-RF03 2.0 Non-Interventional Statistical Analysis Plan For Secondary Data Collection Study 01-Jun-2020 Page 5 of 17 cohorts: a) patients from Study C4181005 who have completed Visits 1 through 11 (at D183); b) patients from Study C4181001 who meet the eligibility criteria for Study C4181005 and have at least 6 months follow-up data. Eligible patients from Study C4181001 will be included as potential external controls for patients in Study C4181005, using propensity score methodology.

This pilot study has the potential to demonstrate the feasibility of Study C4181001 as concurrent external controls and provide viable study design options for the recifercept pivotal trial. It will also provide information on the efficacy of recifercept compared to clinical practices in the real world. Having an external control arm in the trial allows for increased efficiency and decreased product development time.

Study population

This retrospective cohort study will include achondroplasia patients from Study C4181005 and those from Study C4181001 who meet the inclusion and exclusion criteria of Study C4181005. Study C4181005 is a single-arm trial to evaluate the safety and tolerability of recifercept doses and dosing regimen, and efficacy to increase height growth in achondroplasia patients. Study C4181005 will include approximately 63 children with achondroplasia aged 3 months to 10 years (inclusive) with Tanner Stage 1. who are enrolled and randomized to receive one of three doses of recifercept (1mg/kg once-weekly, 2mg/kg twice-weekly, or 1.5mg/kg once-daily) subcutaneously for 12 months. Demographics, medical history, anthropometric measurements, and patientreported outcomes in functional status and quality of life are collected approximately every 3 months. Study C4181001 is a prospective natural history study to collect the longitudinal anthropometric and disease-related complication data in children with achondroplais. It will include approximately 300 achondroplasia patients aged 0-15 years with Tanner Stage I recruited from global sites. Patient data will be collected at baseline and at every 3-month interval visits, for a maximum of 5 years. Further details on data sources are presented in Table 1.

Data source

• For this pilot study, the data in Table 9.3 from C4181001 and C4181005 will be pooled to create a single dataset. With respect to patients the component datasets will be mutually exclusive – that is, there are no patients common to both studies.

This retrospective cohort external control arm study will include achondroplasia patients from Study C4181005 and those from Study C4181001 who meet the inclusion and exclusion criteria of Study C4181005. Study C4181005 is a single-arm trial to evaluate the safety and tolerability of recifercept doses and dosing regimen, and efficacy to increase height growth in achondroplasia patients. Study C4181005 will include approximately 63 children with achondroplasia aged 3 months to 10 years (inclusive) with Tanner Stage 1, who are enrolled and randomized to receive one of three doses of recifercept (1mg/kg once-weekly, 2mg/kg twice-weekly, or 1.5mg/kg once-daily)

PFIZER CONFIDENTIAL

CT24-WI-GL03-RF03 2.0 Non-Interventional Statistical Analysis Plan For Secondary Data Collection Study 01-Jun-2020 Page 6 of 17 subcutaneously for 12 months. Demographics, medical history, anthropometric measurements, and patient-reported outcomes in functional status and quality of life are collected approximately every 3 months. Study C4181001 is a prospective natural history study to collect the longitudinal anthropometric and disease-related complication data in children with achondroplais. It will include approximately 300 achondroplasia patients aged 0-15 years with Tanner Stage I recruited from global sites. Patient data will be collected at baseline and at every 3-month interval visits, for a maximum of 5 years.

Table 1. Data sources*

•		•	Recifercept phase 2 Clinical Trial (Study C4181005)	•	Natural History Study (Study C4181001)
•	Study population	•	3m-10y, Tanner Stage 1	•	0-10y, Tanner Stage 1
•	Study duration	•	12 months	•	Up to 5 years
•	Visit interval	•	- Medical history collected at baseline	•	- Complications collected every 3 months
		•	- Anthropometric measurements every 3 months	•	- Anthropometric measures every 3 months
		•	- Biomarkers baseline, D1, D4, D8, D15, D29, M2, M3, M6, M9, M12	•	- Biomarkers sample taken once annually
		I			
•	Sample size	•	63 patients	•	300 patients anticipated
•	Primary objective	•	- Evaluate the safety and tolerability of recifercept doses and dosing regimens in participants aged ≥ 2 to <11 years with achondroplasia	•	- Collection of longitudinal anthropometric and disease- related complication data in children with achondroplasia
		•	- Assess efficacy of recifercept to increase height growth in children with achondroplasia		
•	Secondary outcomes	•	- To evaluate the pharmacokinetics of recifercept in participants aged ≥ 2 to <11 years with achondroplasia	•	- Investigation of potential serum biomarkers in children with achondroplasia
		•	- To assess efficacy of recifercept to improve ahondroplasia-related complications		

PFIZER CONFIDENTIAL

CT24-WI-GL03-RF03 2.0 Non-Interventional Statistical Analysis Plan For Secondary Data Collection Study 01-Jun-2020 Page 7 of 17

Treatment/cohort labels

Treatment are determined which protocol each participant is in and will be reported as such.

Protocol	Treatment	Label
C4181001	Not treated	
C4181005	Treated	Recifercept

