4 ANALYSIS SETS/POPULATIONS

4.1 FULL ANALYSIS SET

The Full Analysis set includes all patients who met the inclusion & exclusion criteria listed below.

Inclusion criteria

All patients from Study C4181005 who have completed Visits 1 through 11 (at D183) will be included in this project.

To construct a concurrent external control from Study C4181001, patients from Study C4181001 will need to meet the following eligibility criteria from Study C4181005:

- Documented, confirmed genetic diagnosis of achondroplasia from historical medical records (test must have been performed at a laboratory fully accredited for genetic testing under local regulations)
- Aged \geq 3 months to <11 years (up to the day before 11th birthday inclusive) at time of enrollment into Study C4181001
- *Have completed at least 2 valid height/length measurements (at least 3 months apart)*
- Assessed for Tanner stage 1 during physical examination before or at enrollment into Study C4181001 (must include assessment of breast development for females, or testicular stage for males)
- Able to stand independently for height measurements (if ≥ 2 years of age at enrollment); If aged < 2 years at enrollment, has a documented historical MRI brain/cervical spine performed in the previous 12 months.

PFIZER CONFIDENTIAL

CT24-WI-GL03-RF03 2.0 Non-Interventional Statistical Analysis Plan For Secondary Data Collection Study 01-Jun-2020 Page 9 of 17 • *Have at least 6 months of available follow-up data after enrollment into Study C4181001*

Exclusion criteria

- Presence of severe obesity (BMI > 95% percentile on Hoover-Fong BMI charts)
- Body weight <7kg or >30kg
- *History of chronic kidney disease (CKD) or renal impairment*
- History of receipt of any treatment that are known to potentially affect growth (including oral steroids > 5 days in the last 6 months before enrollment, high dose inhaled corticosteroids (>800 mcg/day beclametasone equivalent) and medication for attention deficient hyperactivity disorder)
- Less than 6 months since fracture or surgical procedure of any bone determined from the baseline visit date.
- Presence of any internal guided growth plates/devices
- *History of removal of internal guided growth plates/devices within 6 months prior to enrolment*

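### The plan says the two studies share no patients but also that every trial child came from the natural history study, and no written rule keeps such a child out of the control pool

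*SAP*

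**What the plan says.** On overlap, the Data source part of SAP 2.1 states: "With respect to patients the component datasets will be mutually exclusive – that is, there are no patients common to both studies". Protocol 9.7 has the same statement, including the reason given, that "there are no patients common to both studies".

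On where the trial children came from, the SAP Introduction states: "All patients participating in Study C4181005 were or will be recruited from Study C4181001". Protocol sections 4 and 7 repeat it. All of this is current text, not amendment history.

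On the cohorts, SAP 2.1 says "The study population will include two independent study" cohorts. It defines the control source as "patients from Study C4181001 who meet the eligibility criteria for Study C4181005 and have at least 6 months follow-up data", and SAP 4.1 repeats the follow-up requirement: "Have at least 6 months of available follow-up data after enrollment into Study C4181001".

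On sizes, both documents plan 63 trial children. SAP Table 1 gives "300 patients anticipated" for C4181001.

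On identification, Protocol 10.1 says: "This study involves data that exist in anonymized structured format". Neither document describes an identifier that follows a child from one study to the other.

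**The concern.** The plan gives the absence of shared patients as the ground for having non-overlapping datasets. Its own account of recruitment contradicts that ground. Because exclusivity is asserted as a fact, no step brings it about.

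Under the written criteria, a child's untreated C4181001 record could serve as a control while the same child's C4181005 record counts as treated. The two groups would then not be independent, and the analysis models have no term for that. The documents also do not say whether C4181001 follow-up stops when a child enters the trial. If it continues, heights measured on treatment could be carried under the untreated label.

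**Working it through.** No power or alpha figure is involved. The check is one of consistency, followed by simple counts.

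**1. The two statements.** If every C4181005 child was recruited from C4181001, the trial children are a subset of the C4181001 children. The patients common to both studies are then all the trial children, not none. The no-overlap statement can hold only if a child is no longer counted in C4181001 after moving to the trial. Neither document says so.

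**2. Is there a removal step anywhere?**
- SAP 2.1, control definition: eligibility plus 6 months of follow-up; nothing on later trial entry.
- SAP 4.1, inclusion and exclusion lists: no criterion removes C4181005 participants or cuts off C4181001 data at trial entry.
- SAP 2.1, treatment labels: set by the protocol the participant is in; no rule for a child with records under both.
- SAP 10.3, code: no de-duplication.
- Protocol 9.8: no quality control beyond that of the two source studies.

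**3. Could a trial child's C4181001 record qualify?** The control criteria are presented as those of the trial, so many trial children could plausibly meet them. The follow-up rule may fail for some: it asks for 6 months, while the listed height history is two measurements at least 3 months apart. A child who entered the trial soon after the second measurement might fall short. Where a record does qualify, SAP 5 sets the untreated baseline at consent and the treated baseline at Day 1, so one child can supply two separate sets of changes from baseline.

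**4. What the models would do (SAP 10.3).**
- Propensity model: a shared child gives two rows with opposite outcomes, treated as independent.
- Matched mixed model: subject is nested within matched set, so a child who falls in two sets is two independent subjects.
- IPW model: `region = allobs` keeps every record. If the subject identifier differs between studies, the child is again two independent subjects. If it is the same, one subject carries both treatment labels and two weights. The documents do not say which applies.

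**5. How many children?** The planned trial size is consistent: 54 + 9 = 63 and 3 × 21 = 63. To appear in both groups, a child must have completed C4181005 Visit 11 (D183) and have at least 6 months of C4181001 follow-up. The number of shared children k therefore satisfies 0 ≤ k ≤ 63 at planned enrollment.

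The share of the control pool is k/E, where E is the number of eligible controls. E is not given. With k at its maximum and E purely assumed:

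| Assumed E | 63/E |
|---|---|
| 200 | 31.5% |
| 150 | 42% |
| 100 | 63% |

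The lower end is 0% in every row, so the documents do not fix the share.

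**The case against.** The best defence is that the main clause in SAP 2.1 is in the future tense and concerns the component datasets. It can be read as a rule for building the pooled file, with each child in one component only. The label rule, which ties a participant to one protocol, fits that reading. On this view the plan already intends the right result, and only the explanatory clause is inaccurate. This stands in part: the intention is there, and double entry is not shown to have occurred. But the sentence rests on a premise the Introduction denies, and no criterion or code carries the intention out.

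It might also be said that the exclusion for growth-affecting treatment catches trial children. Its only stated time window is before enrollment, so a child who joined C4181001 untreated and entered the trial later is not clearly caught.

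Self-matching is limited. Sex and the White indicator are matched exactly, and age is the only other propensity predictor in SAP 10.3. If the 6 months of follow-up precede treatment, the child's control baseline is about 6 months or more before Day 1. Pairing a child with itself is therefore disfavoured on age, though not excluded.

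A reader might infer that the control pool of 300 is overstated, that 63/300 = 21% or about one in five controls are trial children, and that only 300 − 63 = 237 remain. The documents do not support this. The 300 is C4181001's anticipated enrollment, not the control pool, which is what remains after the filters in SAP 4.1. The 237 further assumes full enrollment and that the 63 are counted within the 300; neither is stated. The numerator also shrinks under the 6-month rule.

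**Conclusion.** The contradiction is real and appears in both documents. The written control criteria admit a trial child who has at least 6 months of C4181001 follow-up, so the same child could be in the control pool and in the treated arm. That would contradict the independent cohorts of SAP 2.1 and the between-subject independence assumed by the propensity and mixed models.

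The size is bounded only in number: at most 63 children, assuming planned trial enrollment is not exceeded, and fewer if some lack the C4181001 follow-up or did not complete Visit 11. The share of controls and the direction of any effect on the estimate or its standard error cannot be derived from the documents.

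A reader might also infer that the Objective 1 conclusion is undermined because the pool is smaller than it looks. SAP 7.2.1 decides Objective 1 on standardized mean differences below 0.1, not on pool size. Any effect of shared children on that criterion would be indirect and is not shown.

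**What to change.** 1. Reconcile the recruitment statement (SAP 2; Protocol 4 and 7) with the no-overlap statement (SAP 2.1; Protocol 9.7).
2. Add to SAP 4.1 an exclusion from the control pool of any C4181001 participant who is in the C4181005 cohort, so that each child contributes to one group only, as SAP 2.1 intends.
3. Link subjects across the two studies before pooling. Confirm first that the anonymised data allow this; the documents do not show that they do.
4. Report the number of records removed and the number of eligible controls remaining.
5. Leave the figure of 300 in SAP Table 1 unchanged. It describes C4181001's enrollment.

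Cutting off C4181001 data at trial entry is an alternative, but it leaves the same child in both groups and so does not deliver the stated exclusivity.

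The cost is some wording and one linkage step, whose effort depends on what identifiers survive anonymisation. If the datasets are already disjoint, a sentence saying how this was achieved is enough. The statistical price is a smaller control pool, and controls chosen partly on a later event, namely not having entered the trial. That selection should be stated as a limitation alongside those in Protocol 9.9.
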